## 7.2. Participant Discontinuation/Withdrawal from the Study

Discontinuation is expected to be uncommon.

A participant may withdraw from the study:

- at any time at the participant's own request
- at the request of the participant's designee (for example, parents or legal guardian)
- a participant will be withdrawn from the study in case of inadvertent enrollment
- at the discretion of the investigator for safety, behavioral, compliance, or administrative reasons
  - If the participant becomes pregnant during the study (see Section [8.3.2](#) for additional details)
- if enrolled in any other clinical study involving an investigational product, or enrolled in any other type of medical research judged not to be scientifically or medically compatible with this study
- if the participant, for any reason, requires treatment with a therapeutic agent that is prohibited by the protocol and has been demonstrated to be effective for treatment of the study indication. In this case, discontinuation from the study occurs prior to introduction of the new agent.

At the time of discontinuing from the study, if possible, the participant will complete procedures for an ED visit and post-treatment follow-up, if applicable, as shown in the SoA. If the participant has not already discontinued the study intervention, the participant will be permanently discontinued from the study intervention at the time of the decision to discontinue the study.

If the participant withdraws consent for disclosure of future information, the sponsor may retain and continue to use any data collected before such a withdrawal of consent. If a participant withdraws from the study, the participant may request destruction of any samples taken and not tested, and the investigator must document this in the site study records.

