### 2.2. Background

Obstructive sleep apnea is a serious medical condition with a limited number of therapeutic options and high unmet need. OSA is a well-established risk factor for morbidity and mortality from CV and other metabolic diseases; further, it negatively affects daily life of patients (Tietjens et al. 2019; Gottlieb and Punjabi 2020).

Treatments for OSA include behavioral measures like weight loss programs, medical devices such as PAP, oral appliances or hypoglossal nerve stimulation, and surgery, including bariatric surgery in people living with obesity and OSA. Weight loss through caloric restriction and lifestyle interventions improves AHI, cardiometabolic comorbidities, and quality of life.

Although a limited number of studies have investigated the effect of pharmacological weight-loss therapy, their results support that adding weight-loss medication to lifestyle intervention reduces AHI and improves sleep quality and possibly other OSA-related outcomes. As such, standard of care recommends a prioritization of weight loss for patients with OSA and obesity or who are overweight, including consideration for FDA-approved antiobesity pharmacotherapy (Hudgel et al. 2018). Bariatric surgery is available for patients with severe obesity and can dramatically improve OSA (Currie et al. 2021). However, such surgical procedures are associated with greater risk for perioperative and postoperative complications (Oppenner et al. 2016).

Positive airway pressure is the first-line treatment for moderate-to-severe and symptomatic mild OSA. Despite good clinical efficacy for the signs and symptoms of OSA, randomized controlled studies in PAP therapy have failed to show improvements in nonsleep-related outcomes linked to OSA such as stroke, heart attack, diabetes and depression (AHRQ 2021). It is thought inadequate PAP therapy adherence may explain why randomized clinical trials have failed to demonstrate benefit (Gottlieb and Punjabi 2020). Nonadherence to PAP therapy is a major clinical challenge

and studies have shown wide variability in adherence, ranging from 29% to 83% (Weaver and Grunstein 2008). Currently, there are only few pharmacologic alternatives indicated for symptoms in patients with OSA and none are disease modifying.

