## 6.8. Concomitant Therapy

Participants will be permitted to use concomitant medications that they require during the study, except certain medications (Section 6.8.2) that may interfere with the assessment of efficacy and safety characteristics of the study treatments.

Investigative-site staff will inform participants that they must consult with the investigator or a designated site staff member upon being prescribed any new medications during the study. This may not be possible when initiated for treatment of medical emergencies, in which case, the participant will inform the investigator or a designated site staff member as soon as possible.

Nonstudy medications taken by participants who are screened but not randomly assigned to study intervention will not be reported to Lilly unless an SAE or AE occurs that the investigator believes may have been caused by a study procedure.

Any medication or vaccine (including over-the-counter or prescription medicines, vitamins, and/or herbal supplements, or other specific categories of interest) that the participant is receiving at the time of screening or receives during the study must be recorded along with:

- Reason for use
- Dates of administration including start and end dates

The medical monitor should be contacted if there are any questions regarding concomitant or prior therapy.

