### 6.8.2. Prohibited Concomitant Medications

The following medications are prohibited during the study:

- DPP-4 inhibitors
- Open-label GLP-1R agonists
- Stimulants (for example, modafinil, armodafinil, solriamfetol, pitolisant, amphetamine, dextroamphetamine, dextmethylphenidate, methylphenidate, and lisdexamfetamine)
- medications that may cause significant weight gain (such as, but not limited to, paroxetine, tricyclic antidepressants, atypical antipsychotic and mood stabilizers).
- Medications that may cause weight loss (such as, but not limited to, liraglutide, semaglutide, orlistat, sibutramine, phenylpropanolamine, mazindol, phentermine, lorcaserin, naltrexone/bupropion, phentermine/topiramate combination, pramlintide, zonisamide, and topiramate)
- OTC, herbal, or supplemental medications that, in the opinion of the investigator, may interfere with the study
- hypnotics, mirtazapine, opioids, trazodone, pramlintide, sibutramine, orlistat, and zonisamide
- Systemic glucocorticoid therapy, per discussion with sponsor
- Use of any over-the-counter or prescription medications that could affect the evaluation of excessive sleepiness, per investigator discretion (such as, but not limited to, CBD oil, THC, etc.)
- Any glucose-lowering medication, including metformin

In addition,

- Active device treatment of OSA other than PAP therapy (for example, dental appliance), or other treatment that, in the opinion of the investigator, may interfere with study outcomes.

Participants who initiate and will not or cannot discontinue a prohibited medication, device, or other treatment will be permanently discontinued from study intervention per Section 7.1.

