### 7.1. Discontinuation of Study Intervention

When necessary, a participant may be permanently discontinued from study intervention. If so, the participant will remain in the study and follow procedures for remaining study visits, as shown in the SoA.

A participant who prematurely discontinues study intervention is strongly encouraged to remain in the study for safety and efficacy assessments through the treatment period and post-treatment follow-up.

If a participant who discontinues the double-blind study treatment prematurely declines to complete the remaining scheduled study visits, then the participant should complete the early ED procedures indicated in the SoA. Participants should be encouraged to come back for the last treatment visit (Visit 11) to complete the end-of-treatment phase procedures and return for the post-treatment follow-up Visit 801.

Possible reasons leading to permanent discontinuation of study intervention:

- **participant decision**
  - the participant requests to discontinue study intervention
- **clinical considerations**
  - initiation of a prohibited medication (Section 6.8.2), if participants will not or cannot discontinue them
  - BMI  $\leq 18.5 \text{ kg/m}^2$  is reached at any time during the treatment period, study intervention discontinuation should be considered
  - TEAE
    - intolerable GI symptoms despite management (Section 6.5.1)  
*Note:* The investigator should contact the Sponsor CRP to discuss whether it is medically appropriate for the participant to continue study treatment.
    - significant elevation of calcitonin

- If the investigator determines that a systemic hypersensitivity reaction has occurred related to study intervention administration, the participant may be permanently discontinued from the study intervention, and the sponsor's designated medical monitor should be notified. If the investigator is uncertain about whether a systemic hypersensitivity reaction has occurred and whether discontinuation of study intervention is warranted, the investigator may consult the sponsor
- occurrence of any other TEAE, SAE, or clinically significant finding for which the investigator believes that permanent study intervention discontinuation is the appropriate measure to be taken
- Diagnosis of
  - T1DM
  - Thyroid C-cell hyperplasia, MTC or MEN Syndrome type 2 after randomization
  - acute or chronic pancreatitis

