### Overall Rationale for the Amendment:

This amendment includes the addition of a key secondary objective, “Change in AHI”. The endpoint for key secondary objective “Change in SBP” and other secondary objective “Change in DBP” has been updated to Week 48 from Week 52. Changes have been made to the Schedule of Activities to reflect the synchronization of timing of C-SSRS to PHQ-9.

Protocol changes have been made as outlined in the following table.

Section # and Name	Description of Change	Brief Rationale
1.1. Synopsis and 3. Objectives, Endpoints, and Estimands	Key Secondary Objectives: Added “Change in AHI” as a key secondary objective with endpoint “Change in AHI”	To align with recommendations from health authority.
	Key Secondary Objectives: Moved “change in SBP” to “From baseline to Week 48” section	BP will be assessed at Week 48 because PAP suspension at Week 52 may confound BP assessment.
	Added footnote a “BP will be assessed at Week 48 because PAP suspension at Week 52 may confound BP assessment”.	For additional information.
1.3. Schedule of Activities	Removed text, “Note: Visit 10 is eligible to be conducted remotely (that is, by telephone, IT-assisted virtual visit, or in combination with on-site visit) at the direction of the sponsor, according to local laws and regulations.”	Vital signs will be measured at Week 48, so this visit will be on site.

Section # and Name	Description of Change	Brief Rationale
	“Fasting Visit” row: Removed text, “If V10 is remote, then the visit will not be fasting.”	This instruction is no longer applicable.
	“Weight” row: Removed text, “If V10 is remote, then weight will not be obtained at the visit.”	This instruction is no longer applicable.
	“Vital signs” row: Removed text, “If V10 is remote, vital signs will not be obtained at the visit.”	This instruction is no longer applicable.
	“Symptom-directed physical assessment” row: Removed text, “If V10 is remote, then symptom-directed physical assessment will not be done at the visit.”	This instruction is no longer applicable.
	Removed “Schedule Sleep Center Study for PSG” and “Sleep Center Study for PSG” from ED visit.	Sleep study is not required for participants who discontinue early.

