**Figure GPIF.2.1****Graphical testing scheme for Study GPIF.**

3. Analysis Sets

Table GPIF.3.1 describes the populations that will be used for statistical analyses within each ISA of the master protocol. Additional intervention-specific populations for analyses may be described in the respective ISA.

Table GPIF.3.1. Description of Analysis Population

| Analysis Population | Description |
|---------------------------------|---|
| Entered | All participants who sign informed consent. |
| Randomized | All participants who are randomly assigned a study treatment (double-blind). |
| Modified intent-to-treat (mITT) | All randomized participants who are exposed to at least 1 dose of study intervention. |

Table GPIF.3.2. Description of Analysis Data Point Sets

| Analysis Set | Description |
|-----------------------------|---|
| Full analysis set (FAS) | Data obtained during treatment period of set of participants from the mITT population, regardless of adherence to study intervention. |
| Efficacy analysis set (EAS) | Data obtained during treatment period of set of participants from the mITT population, excluding data after discontinuation of study intervention (last dose + 7 days) and for ISA1, excluding data after initiating PAP therapy. |
| Safety analysis set (SS) | Data obtained during treatment and safety follow-up period of set of participants from the mITT population, regardless of adherence to study intervention. |

Abbreviations: EAS = efficacy analysis set; FAS = full analysis set; ISA = intervention-specific appendix; mITT = modified intent-to-treat; PAP = positive airway pressure; SS = safety analysis set.

4. Statistical Analyses

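### Protocol 7.2 removes participants from the study before they start a prohibited treatment effective for OSA, so Week 52 AHI values that the primary treatment-regimen estimand needs are missing by rule

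*Protocol*

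**What the plan says.** Two rules in the protocol deal with prohibited treatment.

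- **Section 7.2** (repeated for Germany in 10.11.1) lists reasons for leaving the study. One is needing a prohibited agent that has been shown to be effective for the study indication. It ends: "In this case, discontinuation from the study occurs prior to introduction of the new agent". The participant then has, if possible, an early-discontinuation visit and post-treatment follow-up.
- **Section 6.8.2** says: "Participants who initiate and will not or cannot discontinue a prohibited medication, device, or other treatment will be permanently discontinued from study intervention", and refers to 7.1. Section 7.1 says of permanent discontinuation of study drug: "If so, the participant will remain in the study and follow procedures for remaining study visits, as shown in the SoA".

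Section 6.8 tells participants that "they must consult with the investigator or a designated site staff member upon being prescribed any new medications during the study". PAP lies outside both rules, because the device prohibition in 6.8.2 reads "Active device treatment of OSA other than PAP therapy".

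The Schedule of Activities places post-baseline polysomnography at Visits 7 and 11 (Weeks 20 and 52) only. Amendment b took it out of the early-discontinuation visit with the rationale "Sleep study is not required for participants who discontinue early".

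On the analysis side, SAP 1.1.1 makes the treatment-regimen estimand primary for the FDA application, on or off randomized treatment and with no intercurrent events. SAP Section 3 defines the full analysis set as "Data obtained during treatment period of set of participants from the mITT population, regardless of adherence to study intervention". SAP 4.1 aims to limit missing data by keeping those who stop study drug in the study. Table GPIF.4.2 imputes the remaining missing values from same-arm participants who stopped study drug but have a Week 52 value, or by placebo-based imputation if those are too few.

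**The concern.** Whether a Week 52 AHI is collected depends on the order of events and not on anything clinical. A participant who consults the site before starting the drug, as 6.8 asks, falls under 7.2 and is lost to follow-up. One who starts first and then declines to stop is kept. The protocol gives no reason for treating them differently.

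The realistic triggers are off-study weight-loss drugs. Section 6.8.2 prohibits them, naming liraglutide and semaglutide among others. Section 2.2 says, on the basis of a limited number of studies, that "adding weight-loss medication to lifestyle intervention reduces AHI and improves sleep quality". It also says that standard of care includes considering antiobesity drugs.

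Participants who leave under 7.2 cannot serve as donors in the retrieved-dropout imputation. Outcomes on an effective new agent are therefore under-represented among the imputed values, although some donors may be on such an agent or on PAP. If use of these agents is commoner on placebo, the treatment effect is overstated. If it is commoner among tirzepatide participants who stopped for intolerance, the effect is understated. The two-way tipping-point analysis that could explore this is optional (SAP 4.4.1.2). The efficacy estimand is unaffected, because it excludes data after study drug is stopped in any case.

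**Working it through.** **Is the value lost?** The same drug under the two rules:

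| | Consults first (7.2) | Starts first (6.8.2, 7.1) |
|---|---|---|
| Study drug | stopped | stopped |
| Study participation | ends before the agent starts | continues |
| Visits | early-discontinuation visit and follow-up, if possible | all remaining visits |
| Week 52 polysomnogram | none scheduled | scheduled at Visit 11 |
| Treatment-regimen analysis | imputed | observed, and a possible donor |

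Study drug stops in both columns, so leaving the study adds no protection against combined use. It only ends data collection.

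**The plan's own figure.** Inputs from Protocol 9.5: 103 per arm, 50-point difference in percent change in AHI, SD 50 points, 25% dropout, two-sided alpha 0.05.

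- Completers per arm: 103 × 0.75 = 77.25, taken as 77.
- SE of the difference: 50 × √(2/77) = 8.1 points.
- Two-sided t-test power: 0.99999. The stated floor of at least 90% is met; 22 completers per arm would suffice, or 30 after allowing for 25% dropout.

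**Size of the bias, events per hour.** The documents give no rate of use and no agent effect, so these are assumed. Let kP and kT be the numbers leaving under 7.2 on placebo and tirzepatide, d the agent's reduction in AHI, and q the share of donors on an effective agent, taken as equal in both arms:

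overstatement of the effect = (kP − kT) × d × (1 − q) / 103

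- One case, q = 0: 5/103 = 0.05 for d = 5; 15/103 = 0.15 for d = 15.
- kP = 5 (about 5% of an arm), kT = 0, q = 0: 25/103 = 0.24 to 75/103 = 0.73.
- kP = 0, kT = 5, q = 0: −0.24 to −0.73.
- kP = kT: 0.
- kP = 5, kT = 0, q = 0.5: 0.12 to 0.36.

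**On the planning scale, percentage points.**

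- Five placebo cases each mis-imputed by 25 points: 5 × 25/103 = 1.2. The difference goes from 50 to 48.8 and power is 0.99998.
- Wider range: a net excess on placebo of 1% to 10% and an agent effect of 10 to 50 points give 0.01 × 10 = 0.1 to 0.10 × 50 = 5.0. At a difference of 45, power is 0.99986.
- Another 10% missing on top of 25% leaves 66 per arm and power 0.99992 at 50 points.

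**The case against.** The strongest counter-arguments are these.

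- **The exit may be optional.** The 7.2 list opens by saying a participant may withdraw, so the last sentence could be read as fixing only the timing. But that sentence is unconditional and a site would follow it. If exit was meant to be optional, the wording still needs repair.
- **Participants can return for Visit 11.** Section 7.1 encourages this for people who stop study drug and decline the remaining visits, and anyone leaving under 7.2 also stops study drug. That text is not addressed to 7.2 exits, though, and 7.2 itself offers only the early-discontinuation visit and follow-up. Nothing bars a return, but nothing asks for one.
- **No qualifying agent is named.** This stands in part. Section 2.2 also says that existing drug options for OSA treat symptoms and that none is disease modifying. The trigger is narrow, and reading it to include weight-loss drugs is an inference, though one that the protocol's own background supports.
- **The estimand names only adherence and PAP initiation as part of the treatment condition.** True. The SAP does not say that outcomes on a prohibited OSA-effective agent are wanted. But it defines no intercurrent event for them and takes data on or off treatment, so it gives no ground for excluding them.
- **The missing values are handled and the effect is small.** Both stand. Section 7.2 expects discontinuation to be uncommon, and the sample size allows 25% dropout. Imputation is still second best to a value that could have been measured at a visit already scheduled.

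**Conclusion.** The concern holds. Section 7.2 creates avoidable missing primary data in a group whose Week 52 outcomes the treatment-regimen estimand counts. It treats that group differently from participants in the same position under 6.8.2 and 7.1.

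The likely bias is small, and its direction cannot be settled from the documents. It is 0.24 to 0.73 events/h for five cases all in one arm, half that if half the donors are on an effective agent, and zero if the arms are balanced. These figures rest on assumed numbers of cases, an assumed agent effect and an assumed donor share, and on the participants attending the Week 52 polysomnogram if kept. Power stays above 0.999 in every scenario computed. The case for change is the quality of the primary estimate, not the result of the test.

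**What to change.** In Protocol 7.2 and its copy in the Germany appendix (10.11.1), replace study discontinuation for this case with permanent discontinuation of study intervention under 7.1. State that scheduled assessments, including the Week 52 polysomnogram, continue unless the participant withdraws consent. The new agent is already recorded under 6.8, so no new data item is needed. The change affects data collection only, not which treatment the participant receives.

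The cost is a protocol amendment, with the ethics approval that this requires, and a few more participants attending visits already in the schedule.

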### **7.3. Lost to Follow up**

A participant will be considered lost to follow-up if he or she repeatedly fails to return for scheduled visits and is unable to be contacted by the study site. Site personnel or designee are expected to make diligent attempts to contact participants who fail to return for a scheduled visit or were otherwise unable to be followed up by the site.

## 8. Study Assessments and Procedures

Study procedures and their timing are summarized in the SoA.

Immediate safety concerns should be discussed with the sponsor immediately upon occurrence or awareness to determine if the participant should continue or discontinue study intervention.

Adherence to the study design requirements, including those specified in the SoA, is essential and required for study conduct.

All screening evaluations must be completed and reviewed to confirm that potential participants meet all eligibility criteria. The investigator will maintain a screening log to record details of all participants screened and to confirm eligibility or record reasons for screening failure, as applicable.

### 8.1. Efficacy Assessments

#### 8.1.1. Primary Efficacy Assessment

##### 8.1.1.1. Polysomnography

The primary efficacy assessment in this study is AHI. AHI measurements will be collected via polysomnography.

Polysomnography assessments (including AHI, blood oxygen saturation parameters, PR, sleep parameters) will be performed during 1-night, overnight clinic stays, per the SoA. Data from the PSGs will be read and scored centrally using the AASM 1B hypopnea scoring method (when there is  $\geq 4\%$  oxygen desaturation from pre-event baseline; see Section 10.10, Appendix 10 for definitions) (Hamilton et al. 2021).

The eligibility criteria and AHI related endpoints of the study will be assessed based on central reading of the PSG.

